**Table 1 Background DMD Therapies and Cardiac Medications of Relevance by Class**

Med Type (Natural Data Variable name)	Definition of Generic (Brand Name)
ASO/Exon skipping therapy (aso_yn)	Exondys 51 (eteplirsen) Amondys 45 (casimersen) Viltepso (viltolarsen) Vyondys 53 (golodirsen)
Aldosterone antagonists ( aldosterone_yn)	Eplerenone (Inspra) Finerenone Spironolactone (Aldactone/CaroSpir)
Beta-blocker (bb_yn)	Acebutolol Atenolol (Tenormin) Bisoprolol Metoprolol (Lopressor, Toprol XL) Nadolol (Corgard) Nebivolol (Bystolic) Propranolol (Inderal LA, InnoPran XL) Carvedilol (Coreg)
ACEi /angiotensin converting enzyme inhibitor (taking_ace )	Benazepril (Lotensin) Captopril Enalapril (Vasotec) Fosinopril Lisinopril (Zestril) Moexipril

Med Type (Natural Data Variable name)	Definition of Generic (Brand Name)
	Perindopril Quinapril Ramipril (Altace) Trandolapril
ARB /angiotensin receptor blocker (ARB_YN)	Azilsartan (Edarbi) Candesartan (Atacand) Irbesartan (Avapro) Losartan (Cozaar) Olmesartan (Benicar) Telmisartan (Micardis) Valsartan (Diovan)
Calcium channel blockers (cach_yn)	Amlodipine (Norvasc) Diltiazem (Cardizem, Tiazac) Felodipine (Plendil) Nifedipine (Procardia) Nisoldipine (Sular) Verapamil (Calan, Isoptin, Tarka, Verelan)
Steroids (new_med_steroid_v1— new_med_steroid_V.., steroid_change_type, start_date_steroid )	Prednisone/prednisolone Hydrocortisone (note that hydrocortisone cannot be the cream) Deflazacort (Emflaza) Deflazcort Deflazocort Emflaza Emflaza-Delfazacort Solu-Cortf Agamree/vamorolone
ARNI/angiotensin receptor/neprilysin inhibitor (ARNI_yn)	Sacubitril/Valsartan (Entresto)

#### 14.3.5 Missing data handling

Missing data in natural history collection will not be imputed for PSM analysis.

#### **14.3.6 Analysis Population**

For the DB period, only high dose active and placebo subjects with Month 12 evaluable cardiac efficacy data will be included in the analysis.

For OL, all ifetroban treated subjects in the ITT population will be matched with natural history data.

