11.8.3 Efficacy Analyses

Between-treatment comparisons with respect to the change from baseline in LVEF and the change from baseline in myocardial strain at Month 6 and Month 12 will be performed for the ITT and PP Populations using the Wilcoxon rank sum test. A supportive analysis with missing LVEF at Month 12 imputed by LVEF at Month 6; subjects missing LVEF at both Month 6 and Month 12 will be excluded from this supportive analysis. In line with the current paradigm for the assessment of therapeutic efficacy in rare diseases and specifically DMD using established natural history data ([Liu 2022](#), [US FDA 2019](#), [US FDA 2018](#)), a comparison of the NHS-supplemented placebo group (2:1 NHS to placebo) will also be performed at Month 12 versus the high-dose ifetroban ITT and PP populations for CMR parameters.

Summary statistics for other endpoints will be presented for both the ITT and PP Populations.

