11.8.6 Long-Term Safety and Efficacy Analyses

Subjects that complete the 12-month double-blind portion of the study will be eligible for an optional open label extension consisting of repeatable 12-month periods of treatment with high-dose ifetroban.

Safety will be monitored by continual adverse event reporting and changes in laboratory values as previously described.

For main efficacy endpoints (CMR parameters LVEF and myocardial strain), comparisons with respect to the change from Month 12 in LVEF and the change from Month 12 in myocardial strain at Months 24 and 36 will be performed for the ITT open label population using the Wilcoxon rank sum test. To assess treatment response the double-blind and open label studies, comparisons with respect to the change from baseline in LVEF and the change from baseline in myocardial strain at Months 24 and 36 will be performed for the ITT open label population using the Wilcoxon rank sum test. Subjects missing LVEF at either Month 12 or Month 24 will be excluded from this supportive analysis.

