### **3.6 Analysis Sets**

### **3.6.1 Intention-To-Treat (ITT) Population**

The Intent-To-Treat (ITT) Population will consist of all treated subjects with at least one post-baseline assessment.

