## 4.2 Missing Data

For the primary endpoint and key secondary efficacy endpoints, missing data will not be imputed in the primary analyses. A supportive sensitivity analysis for the Month 12 LVEF endpoint will be conducted where missing LVEF values at Month 12 will be imputed using Month 6 values, if available. Subjects missing LVEF at both Month 6 and Month 12 will be excluded from this supportive analysis. For long-term analyses in the open-label extension, subjects missing data at key timepoints (Month 24, Month 36) will be excluded from the respective analyses. No other imputation will be provided for any endpoint.

Since LVEF is a key efficacy endpoint, the pattern of missing data will be carefully evaluated to assess potential bias. The frequency and reasons for missing LVEF measurements will be

summarized by treatment group to determine whether missingness might be related to treatment or disease progression. If systematic differences in missing data patterns are identified between treatment groups, additional sensitivity analyses may be conducted using multiple imputation methods that account for the potential relationship between the likelihood of missing data and the unobserved outcomes. This would involve creating multiple complete datasets based on observed covariates and outcomes, analyzing each dataset, and combining results according to Rubin's rules. These additional analyses would be considered exploratory and would be used to evaluate the robustness of the primary analysis approach.

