#### **4.5.2 Matching Algorithm**

For the DB period, NHS subjects will be matched to high-dose ifetroban subjects at a 2:1 ratio using a global optimal algorithm based on the nearest neighbor approach without replacement and without caliper. For the open-label period, NHS subjects will be matched to all open-label subjects at a 2:1 ratio using the same methodology.

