#### **14.3.3 OL Matching Inclusion/Exclusion for NH**

Subjects from the NH were selected to reflect the baseline criterion of the CPI-IFE007 study before the propensity score is calculated. The following criteria were applied for matching with the OL subjects:

- Male subjects  $\geq 7$  years old.
- 2 years data of LVEF
- Baseline value LVEF of  $\geq 35\%$  (baseline is month 12 in study)
- Subjects with no history of heart failure.
- No current treatment with givinostat (Duvyzyat®) (Variables: other\_meds\_listed ≠ “givinostat,” “duvyzyat”)
- Live subjects with non-missing cardiac efficacy data (CFB LVEF and CFB Myocardial strain) at baseline and month 12 for OL. Live subjects with non-missing cardiac efficacy data (LVEF and Myocardial strain) at month 12 and month 24 for OL. Missing data will not be imputed.

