#### **14.3.7 Analysis with Natural History Data**

Multiple analyses will be completed using matched NH subjects as a historical comparator. See [Figure 2](#) below for a detailed analysis diagram.

In the DB study (Baseline to Month 12), the tables will be presented by the following treatment groups:

- ifetroban High
- Placebo with supplemented NH

In the OL study, the tables will be presented by:

[figure not shown]
One year data (Month 12 to Month 24):

- All OL
- High to High ifetroban
- Low to High ifetroban
- Ifetroban (High and Low combined)
- Placebo to High ifetroban
- NH

All study two-year data (Baseline to Month 24):

- High to High ifetroban
- NH

**Figure 2** All Study Analyses Diagram

For both the OL and the DB, demographic and baseline characteristics will be summarized for by treatment group including baseline LVEF, concomitant medication usage and propensity score by treatment group for the DB period and the OL period. Summary tables will be provided for the observed value and the change from baseline for each endpoint. In addition, 95% confidence intervals will be presented for each treatment group for the demographic variables and baseline characteristics. For categorical variables, proportion confidence intervals will be created using the binomial approximation.

A listing of natural history subjects' demographic and baseline characteristics will also be included.

For the DB period, the endpoints CFB in LVEF and myocardial strain at 12 Months. For the OL period, the endpoints to be evaluated at the 24 months after treatment are CFB LVEF, CFB myocardial strain, PET, QMT, and accelerometry. All endpoints will be evaluated using the change from baseline will be compared between the ifetroban vs. Placebo or natural history groups using a Wilcoxon rank sum test

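### Open-label comparison with natural history: complete data are required of controls before matching but of treated subjects only at analysis, and the SAP does not say what becomes of an excluded subject's controls

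*SAP*

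**What the plan says.** - **Treated subjects entering the OL match.** SAP 14.3.6: "For OL, all ifetroban treated subjects in the ITT population will be matched with natural history data". The ITT population (SAP 3.6.1) is "all treated subjects with at least one post-baseline assessment", which requires neither OL entry nor a Month 24 CMR. SAP 4.5.2 words the set differently: "NHS subjects will be matched to all open-label subjects at a 2:1 ratio using the same methodology".
- **Controls entering the OL match.** SAP 14.3.3 admits "Live subjects with non-missing cardiac efficacy data (LVEF and Myocardial strain) at month 12 and month 24 for OL". SAP 14.3.1, read literally, says the opposite for both periods: it leaves out NH subjects who do have complete cardiac data at baseline and Month 12.
- **Missing data at analysis.** SAP 4.2: "subjects missing data at key timepoints (Month 24, Month 36) will be excluded from the respective analyses". Protocol 11.8.6 agrees: "Subjects missing LVEF at either Month 12 or Month 24 will be excluded from this supportive analysis".
- **Test.** SAP 14.3.7: change from baseline is "compared between the ifetroban vs. Placebo or natural history groups using a Wilcoxon rank sum test". This test does not use the matched sets.
- **Role.** The protocol synopsis (Historical Comparator Analyses) makes NH data the main comparator for the extension. SAP 4.5.3 labels all NH comparisons supplementary.

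The text reviewed contains no rule for deleting a matched set, re-matching, or re-checking balance after a treated subject is excluded.

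**The concern.** Matching balances the controls against the treated subjects who were matched, not against whichever of them are later analysed. Controls pass the completeness screen before matching; treated subjects meet it only afterwards. A treated subject without a Month 24 CMR therefore leaves the test, while the two controls chosen to resemble him would remain. A drift from 2:1 is harmless in itself. What matters is that the remaining controls may differ from the remaining treated subjects in age, LVEF or background therapy.

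The extension has no concurrent control arm, so this comparison carries its efficacy reading. If the rule for leftover controls is written after the dropouts are known, the choice can be influenced by the data.

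**Working it through.** **1. The plan's own figures.** The documents give no power, OL sample size or NH pool size for this comparison. Their only power statement concerns the double-blind (DB) period: 8 per group, effect size 1.6, two-sided 0.05. Recomputed, it is 84.5% for the t-test (stated as above 85%) and 82.0% for the Wilcoxon test (stated as above 80%). It does not bear on this point.

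**2. Counts.** Assume N subjects enter OL and a share d lacks Month 24 data. For N, 48 is the planned target; 30 is an assumption. For d, the two DB dropout assumptions are borrowed: 10% (SAP 3.4) and 25% (Protocol 11.1). Controls = 2N; analysed n = N(1 − d), rounded; leftover controls = 2(N − n).

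| N | d | Analysed vs controls | Ratio | Leftover controls |
|---|---|---|---|---|
| 48 | 10% | 43 vs 96 | 96/43 = 2.23 | 10 |
| 48 | 25% | 36 vs 96 | 96/36 = 2.67 | 24 |
| 30 | 10% | 27 vs 60 | 60/27 = 2.22 | 6 |
| 30 | 25% | 22 vs 60 | 60/22 = 2.73 | 16 |

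**3. Size of the shift.** Let C and M be the mean expected changes, given the matching covariates, of treated subjects who remain and who are missing. With no drug effect and perfect matching, the controls average (1 − d)C + dM and the analysed treated average C. The difference is d(C − M). For example, with d = 0.25 and a gap of 0.5 SD, it is 0.25 × 0.5 = 0.125 SD. Its sign is the sign of C − M, on which the documents are silent.

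**4. Simulation with direct matching, no drug effect.** Assumed: 48 treated, NH pool of 400, optimal 2:1 matching on one covariate score explaining 25% of the variance in change, an unmeasured factor explaining another 25%, and 1000 runs. Positive values favour ifetroban.

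| Who is lost | Leftovers kept, 10% / 25% loss | Leftovers removed, 10% / 25% loss |
|---|---|---|
| Random | 0.00 / 0.01 SD | 0.00 / 0.01 SD |
| Sicker on matched covariates | +0.07 / +0.13 SD | 0.00 / −0.01 SD |
| Healthier on matched covariates | −0.07 / −0.13 SD | −0.01 / +0.01 SD |
| Sicker on unmeasured factor, both groups | +0.01 / 0.00 SD | 0.01 / 0.00 SD |

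When sicker subjects are lost at 25%, the two-sided rejection rate is 8.4% with leftovers kept and 3.2% with them removed. If incomplete data remove 25% of NH subjects but only 10% of treated subjects on the unmeasured factor, the shift is −0.08 SD, against ifetroban, whether or not leftovers are removed.

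**5. Propensity-score matching, closer to the SAP.** SAP 4.5.1 and 4.5.2 match on a score built from many covariates, without a caliper, so a low-LVEF subject's controls need not have low LVEF. Assumed: 40 OL subjects, pool of 250, eight binary drug covariates, yearly change depending on LVEF at 0.1–0.3 points per point, and 15–25% missing, more often at low LVEF. With all controls kept, the net shift was 0.03–0.28 LVEF points towards ifetroban; with leftovers removed, it was 0.01–0.17. The effect of keeping leftovers was 0.03–0.11, against 0.09–0.42 with direct matching on the same inputs. A further propensity-score simulation, also on assumed inputs, gave 0.04–0.39 with all controls kept, 0.00–0.12 with leftovers removed, and 0.02–0.21 when only evaluable subjects were matched.

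**The case against.** **The text may already intend symmetry.** No section says that leftover controls stay; that is read from silence and an unpaired test. The DB list parallel to SAP 14.3.3 contains an item about trial subjects, so the completeness rule may have been meant for both sides. SAP 6.4 speaks of subjects who complete 12, 24 and 36 months. Figure 2 and the separate programming specifications might settle it. This stands as a reason for caution, but SAP 14.3.6 as written points the other way.

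**A reader might infer that the comparison is biased towards ifetroban.** The documents do not support that. Loss of sicker subjects is plausible, since Protocol 9.1 lists death and new medical conditions among the reasons for termination, but nothing says who will lack Month 24 data. Selecting surviving, complete controls can work against the drug.

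**A reader might infer a larger shift.** Direct matching on LVEF and age gave 0.1–0.6 points in one simulation, but that is not the SAP's matching method.

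**A reader might take the DB sentence in SAP 14.3.6 as a rule that the OL period lacks.** That sentence governs who is analysed, not who is matched, and OL subjects with missing data are also excluded from analysis.

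**A reader might see the same break elsewhere.** Protocol 11.8.3 compares the supplemented placebo group "versus the high-dose ifetroban ITT and PP populations for CMR parameters". The protocol matches NH subjects to placebo, so restricting high dose to per-protocol removes no matched partner. The issue arises only under the SAP's matching to high dose, which is a separate conflict. SAP 14.3.7 sets several OL columns beside one NH group, but SAP 4.5.3 describes the comparison as all OL against NH. Both are secondary.

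**Safeguards exist.** SAP 14.3.8 plans a covariate-adjusted comparison with the whole eligible NH cohort, SAP 14.3.7 tabulates baseline LVEF and propensity score by group, and SAP 4.2 summarises missing LVEF and allows multiple imputation. These could reveal or partly offset an imbalance, but they do not define the matched comparison, and the adjustment model is not specified.

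**Conclusion.** The point holds as an unaligned rule and a missing rule. Completeness is applied at different stages on the two sides, and the handling of an excluded subject's controls is unstated, so the 2:1 ratio and the covariate balance reached at matching need not survive into the test.

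The effect is conditional and modest: roughly 0.04 to 0.4 LVEF points towards ifetroban if subjects with worse prognosis on the matching covariates are the ones missing, none if loss is random, and reversed if healthier subjects are lost. This range rests on assumed OL size, NH pool, missing rate, dropout mechanism and dependence of change on LVEF, and only part of it comes from the leftover controls.

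Confidence is high on the asymmetry and low on the direction. Severity is moderate: the primary endpoint is safety and the comparison is not randomised, but it is the extension's main efficacy contrast and the gap is easy to close.

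**What to change.** 1. In SAP 14.3.6, require OL treated subjects to have evaluable data at both visits of the comparison before they are matched.
2. Carry a matched-set identifier. For each endpoint and visit, keep only controls whose treated partner is in that analysis. This is still needed after step 1, because pulmonary function, QMT, accelerometry and Month 36 data will be missing for different subjects.
3. Show the all-matched version as a sensitivity analysis, and tabulate covariate balance for the analysed sets.
4. In the same edit, reconcile SAP 4.5.2 (all OL subjects), 14.3.1 (the literal exclusion of complete NH subjects), 14.3.3 and 14.3.6 (ITT population).

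The cost is SAP wording, a filter on the set identifier and a slightly smaller control group: at 25% loss, 36 against 72 instead of 36 against 96. With direct matching, removing leftovers brought the shift they caused to about zero (within 0.015 SD). With propensity-score matching some imbalance remains, which is why balance should be reported. The change does not remove bias from selecting controls who are alive with complete data.

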#### **14.3.7 Analysis with Natural History Data**

Multiple analyses will be completed using matched NH subjects as a historical comparator. See [Figure 2](#) below for a detailed analysis diagram.

In the DB study (Baseline to Month 12), the tables will be presented by the following treatment groups:

- ifetroban High
- Placebo with supplemented NH

In the OL study, the tables will be presented by:

[figure not shown]
One year data (Month 12 to Month 24):

- All OL
- High to High ifetroban
- Low to High ifetroban
- Ifetroban (High and Low combined)
- Placebo to High ifetroban
- NH

All study two-year data (Baseline to Month 24):

- High to High ifetroban
- NH

**Figure 2** All Study Analyses Diagram

For both the OL and the DB, demographic and baseline characteristics will be summarized for by treatment group including baseline LVEF, concomitant medication usage and propensity score by treatment group for the DB period and the OL period. Summary tables will be provided for the observed value and the change from baseline for each endpoint. In addition, 95% confidence intervals will be presented for each treatment group for the demographic variables and baseline characteristics. For categorical variables, proportion confidence intervals will be created using the binomial approximation.

A listing of natural history subjects' demographic and baseline characteristics will also be included.

For the DB period, the endpoints CFB in LVEF and myocardial strain at 12 Months. For the OL period, the endpoints to be evaluated at the 24 months after treatment are CFB LVEF, CFB myocardial strain, PET, QMT, and accelerometry. All endpoints will be evaluated using the change from baseline will be compared between the ifetroban vs. Placebo or natural history groups using a Wilcoxon rank sum test

#### 14.3.8 Sensitivity Analysis

A sensitivity analysis will be performed for the DB period, by re-selecting natural history subjects (Placebo:High-Dose ifetroban) using the average Treatment Effect (ATE), by applying the inverse probability of treatment weighting (IPTW). These weights will create pseudo-population of the untreated, which has the same covariate distribution as the treated. While every treated subject received a weight of  $[1/PS]$ , every untreated subject is weighted by  $[1/(1-PS)]$ . An additional exact matching analysis will be explored for feasible categorical variables.

Two separate sensitivity analyses will be performed using caliper 0.2 and using exact matching.

An additional sensitivity analysis will be performed comparing the ifetroban treatment groups to the entire eligible NH cohort (before matching) to evaluate the robustness of findings from the matched analysis. This will help assess whether the treatment effect observed in the matched comparison remains consistent when compared against the broader NH population. This analysis will use appropriate covariate adjustment in the statistical models to account for baseline differences between groups rather than relying solely on matched pairs.
